9.2. Analysis sets

Table 19 Analysis sets (Amended: 13 December 2022)

Analysis set	Description
Enrolled	Participants who were randomized or received study intervention or have undergone an invasive procedure.
Exposed	All participants who received a study intervention. Analysis per group is based on the study intervention administered.
Per Protocol	All eligible participants: 
 • who received at least one study intervention as per protocol in control group and all study interventions in the Co-Ad group, • had immunogenicity results pre- and post-dose, • complied with blood draw intervals (refer to Table 3 and Table 4) (contribution of participants to Per Protocol set at specific timepoint will be defined by timepoint), • without intercurrent medical conditions that may interfere with immunogenicity and, • without prohibited concomitant medication/vaccination.

9.2.1. Criteria for elimination from analysis

If the participant meets one of the criteria mentioned below or ones listed in the Section [7.1.1](#), (contraindication to subsequent vaccination) or [5.2.1](#) (medical conditions) or [5.2.2](#) (concomitant therapy), he/she may be eliminated from per protocol analysis.

In case of unplanned administration of any medication mentioned in Section [5.2.2](#) during the study, this will be considered as a protocol deviation and the participant may be eliminated from the Per Protocol set (PPS).

Participants may be eliminated from the PPS for immunogenicity if, during the study, they incur a condition that has the capability of altering their immune response (intercurrent medical condition), or are confirmed to have an alteration of their initial immune status. Refer to [Glossary of terms](#) for the definition of intercurrent medical conditions.

9.3. Statistical analyses

The Statistical Analysis Plan (SAP) will be developed and finalized before First Subject First Visit (FSFV). This section is a summary of the planned statistical analyses of the primary and secondary endpoints. Supportive analyses, safety and demography summaries will be described in the SAP.

9.3.1. Primary endpoints/estimands analysis (Amended: 13 December 2022)

The primary endpoints/estimands are described in Section [3](#). The confirmatory analyses of non-inferiority will be based on the PPS.

- Method for non-inferiority of the FLU vaccine in terms of HI GMT ratio for each of the FLU vaccine strains at one month after the FLU vaccine dose (i.e., at Day 31 for both groups):

The 2-sided 95% confidence interval (CI) for Group GMT ratio between the FLU vaccine administered alone (Control group) over the RSVPreF3 OA investigational vaccine when co-administered with the FLU vaccine (Co-Ad group) will be derived from an ANCOVA model* on \log_{10} transformed titer.

- Method for non-inferiority of RSV investigational vaccine in terms of RSV-A neutralization antibody GMT ratio at one month after the RSVPreF3 OA investigational vaccine dose (i.e., at Day 31 for the Co-Ad group and at Day 61 for the Control group):

The 2-sided 95% CI for Group GMT ratio between the RSVPreF3 OA investigational vaccine administered alone (Control group) over the RSVPreF3 OA investigational vaccine when co-administered with the FLU vaccine (Co-Ad group) will be derived from an ANCOVA model* on \log_{10} transformed titer.

- Method for non-inferiority of RSV investigational vaccine in terms of RSV-B neutralization antibody GMT ratio at 1 month after the RSVPreF3 OA investigational vaccine dose (i.e., at Day 31 for the Co-Ad group and at Day 61 for the Control group).*

The 2-sided 95% CI for Group GMT ratio between the RSVPreF3 OA investigational vaccine administered alone (Control group) over the RSVPreF3 OA investigational vaccine when co-administered with the FLU vaccine (Co-Ad group) will be derived from an ANCOVA model on \log_{10} transformed titer.*

**The model will include the treatment group and age category (age at vaccination: 65-69, 70-79 or ≥ 80 years) as fixed effects, and the pre-dose \log_{10} -transformed titer as covariate. Missing data will not be replaced. Titors below the assay cut-off will be replaced by half the assay cut-off; titers above the upper limit of quantification (ULOQ) will be replaced by the ULOQ.*

Success criteria for non-inferiority **and testing sequence**:

The following testing sequence will be used:

- Sequence 1:***
 - The upper limit (UL) of the 2-sided 95% CI on the Group GMT ratio (Control group divided by Co-Ad group) for each of the FLU vaccine strains are ≤ 1.5 .

AND

 - The UL of the 2-sided 95% CI on the Group GMT ratio (Control group divided by Co-Ad group) for RSV-A ***neutralizing antibody*** is ≤ 1.5 .
- Sequence 2:***
 - The UL of the 2-sided 95% CI on the Group GMT ratio (Control group divided by Co-Ad group) for RSV-B ***neutralizing antibody*** is ≤ 1.5*

Testing will progress in sequence 2 only if the sequence 1 is a success, so that no further adjustment of alpha is required.

9.3.2. Secondary endpoints/estimands analyses

- Method for evaluation of non-inferiority of the FLU vaccine in terms of HI seroconversion rate (SCR) for each of the FLU vaccine strains at one month after the FLU vaccine dose (i.e., at Day 31 for both groups):
 - The 2-sided 95% CI on group difference in SCR (Control group minus Co-Ad group) will be computed based on the method of Miettinen and Nurminen [Miettinen, 1985].
 - Reference criteria for evaluation of non-inferiority:
The UL of the 2-sided 95% CI on the group difference (Control group minus Co-Ad group) in SCR is $\leq 10\%$ for anti-HI antibodies.
- The other secondary endpoints are described in Section 3. Descriptive analyses of demography, immunogenicity, and safety will be detailed in the SAP.

Table 20 Definitions of SCR, SPR and MGI

Abbreviation/Term	Definition
HI SCR	The percentage of vaccinees who have either a HI pre-dose titer $< 1:10$ and a post-dose titer $\geq 1:40$ or a pre-dose titer $\geq 1:10$ and at least a 4-fold increase in post-dose titer.
HI SPR	The percentage of vaccinees with a serum HI titer $\geq 1:40$ that usually is accepted as indicating protection.
MGI	The geometric mean of the within-participant ratios of the post-dose titer over the pre-dose titer.

HI = hemagglutination inhibition; SCR = seroconversion rate; SPR = seroprotection rate; MGI = mean geometric increase

- Additionally, the Center for Biologics Evaluation and Research (CBER) and Committee for Medicinal Products for Human Use (CHMP) criteria for HI SPR and SCR will be assessed as follows:

CBER's criteria:

- The lower limit (LL) of the 95% CI for SCR should be $\geq 30\%$ in participants ≥ 65 YOA.
- The LL of the 95% CI for SPR should be $\geq 60\%$ in participants ≥ 65 YOA.

CHMP's criteria:

At least one of the 3 following criteria should be met:

- The point estimates of SPR $> 60\%$, SCR $> 30\%$, and MGI > 2.0 for elderly ≥ 60 YOA for each of the antigen strains.

9.4. Interim analyses

9.4.1. Sequence of analyses

The analyses will be performed stepwise:

A final analysis will be conducted once all immunogenicity data (as clean as possible) are available for the primary and secondary endpoints. This final analysis will include immunogenicity and safety data up to Visit 2/Day 31 (Co-Ad group) or Visit 4/Day 61 (Control group). Participants who undergo Visit 2, Visit 3, or Visit 4 assessments out of the allowed visit interval (see [Table 3](#) and [Table 4](#)) may be excluded from the final analysis.

- An EoS analysis with all data (including data obtained until 6 months post-last dose) will be performed.

9.4.2. Statistical considerations for interim analysis

This section is not applicable.

9.5. Sample size determination

The **target enrollment** will be **1028 participants** (514 in the group receiving the RSVPreF3 OA investigational vaccine co-administered with FLU aQIV [Co-Ad group] and 514 in the Control group where RSVPreF3 OA investigational vaccine and FLU aQIV are administered in a sequential manner). This allows to obtain at least **924 evaluable participants** (462 in the Co-Ad group and 462 in the Control group) for the evaluation of the primary objectives, assuming that 10% of the enrolled participants will not be evaluable.

Participants who withdraw from the study will not be replaced.

Each objective will be evaluated with a nominal type I error of 2.5%.

Table 21 Overall power to demonstrate primary objectives: non-inferiority of the immunogenicity of the RSVPreF3 OA investigational vaccine when co-administered with FLU aQIV compared to when administered alone – assuming approximately 462 participants are available in each group (Amended: 13 December 2022)

Endpoint	Standard deviation of \log_{10} concentration	Reference ratio	Non inferiority margin	Type II error	Power
FLU non-inferiority* (1-sided test with alpha=2.5%)					
GMTs HI H1N1 strain	0.6	1.05	1.5	2.5%	97.5%
GMTs HI H3N2 strain	0.6	1.05	1.5	2.5%	97.5%
GMTs HI B/Yamagata	0.6	1.05	1.5	2.5%	97.5%
GMTs HI B/Victoria strain	0.6	1.05	1.5	2.5%	97.5%
RSV-A non-inferiority* (1-sided test with alpha = 2.5%)					
GMTs RSV-A neutralization antibody	0.45	1.05	1.5	0.1%	99.9%
RSV-B Non-inferiority* (1-sided test with alpha = 2.5%)					
GMTs RSV-B neutralization antibody	0.45	1.05	1.5	0.1%	99.9%
Global Type II error to show non-inferiority				~10.0%	
Global power					~90.0%

GMT = geometric mean titer; HI = hemagglutination inhibition; RSV = respiratory syncytial virus

*Pass 2019 alpha = 2.5%, Two-Sample T-Tests for Non-Inferiority Assuming Equal Variance and Equal mean

For RSV: non-inferiority limit = 0.176 ($=\log_{10}[1.5]$).

For each Flu vaccine strain: non-inferiority limit = 0.176 ($=\log_{10}[1.5]$).

Reference Ratio= 0.0212 ($=\log_{10}[1.05]$)

Considering a potential slight interference of 1.05 in true GMTs in both groups with a common population standard error of 0.45 for the RSV-A *and RSV-B neutralization antibodies* and 0.6 for each of the FLU strains in \log_{10} transformed concentration, the study has at least 90.0% power to meet the primary objectives.

Nominal powers to evaluate the secondary objective

The nominal power to evaluate the non-inferiority on SCR for each of the FLU strains is above 86%, depending on the plausible rates.

Table 22 Evaluation of non-inferiority in terms of HI antibody SCR when FLU aQIV is co-administered with the RSVPreF3 OA investigational vaccine compared to FLU aQIV when administered alone assuming approximately 462 participants are available in each group for a range of plausible SCRs (Amended: 13 December 2022)

N evaluable participants per group	Threshold	Plausible rates in Control group**	Type II error	Nominal Power
FLU vaccine: Non-inferiority* in terms of SCR				
462	10%	70%	8.7%	91.3%
462	10%	50%	13.9%	86.1%
462	10%	35%	11.0%	89.0%
462	10%	25%	6.1%	93.9%

SCR = Seroconversion Rate.

*Pass 2019 alpha = 2.5%, for SCR – Non-inferiority: Proportions – Two independent Proportions – Non-Inferiority Tests for the Difference Between Two Proportions.

** SCR observed in the Control group in Zoster-004 study range from 35.3% to 60.9%.

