4.3.1.1. Between groups assessment

- The asymptotic standardized 95% CI for the difference in seroconversion rate (Control group minus Co-Ad group) will be computed at 1 month after the FLU vaccine (i.e., at Day 31 [Visit 2] for both groups).

Reference criteria for evaluation of non-inferiority:

The upper limit of the 2-sided 95% CI on the group difference (Control group minus Co-Ad group) in seroconversion rate is $\leq 10\%$ for anti-HI antibodies.

All between groups analyses of secondary endpoints presented in this section will be descriptive with the aim to characterize the difference in immunogenicity between groups. These descriptive analyses should be interpreted with caution considering that there is no adjustment for multiplicity for these comparisons.

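### Does the stated power of above 86% for SCR non-inferiority need changing because it assumes, without saying so, equal true SCRs in both groups?

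*Protocol*

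**What the plan says.** Protocol 9.5 gives a nominal power for the secondary SCR evaluation: "The nominal power to evaluate the non-inferiority on SCR for each of the FLU strains is above 86%, depending on the plausible rates". Table 22 supports it, "assuming approximately 462 participants are available in each group for a range of plausible SCRs". Its columns are the number per group, the 10% threshold, the Control rate, the type II error and the power. There is no column for the Co-Ad rate or for a true difference. The footnotes identify the calculation ("Pass 2019 alpha = 2.5%, for SCR", under "Non-Inferiority Tests for the Difference Between Two Proportions") and give a source for the rates: "SCR observed in the Control group in Zoster-004 study range from 35.3% to 60.9" per cent. SAP section 5 and its Table 4 carry the same content.

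Earlier in the same section, the power for the primary titer endpoints is stated with an explicit departure from equality: "Considering a potential slight interference of 1.05 in true GMTs in both groups". The only nearby wording about equal means is in the Table 21 footnote and concerns the t-tests on titers.

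The SCR criterion is in Protocol 9.3.2: the upper limit of the two-sided 95% Miettinen-Nurminen interval for Control minus Co-Ad must not exceed 10% "for anti-HI antibodies". SAP 4.3.1.1 gives its standing: "All between groups analyses of secondary endpoints presented in this section will be descriptive", with no multiplicity adjustment.

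**The concern.** Two power statements for the same four strains at the same visit sit a few lines apart. One builds in a small interference and says so; the other builds in none and is silent. Someone who has just read the 1.05 ratio could suppose that the SCR powers also allow for some interference, and could take 86% as a floor for any plausible situation.

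Power at a 10-point margin is sensitive to small true differences, so the silent assumption has weight. If a strain narrowly missed the SCR criterion, a reader relying on 86% would think that less likely by chance than it would be under a slight deficit. At stake is how such a miss is interpreted, not whether the trial is large enough for its primary objectives.

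**Working it through.** **Inputs.** 462 evaluable participants per group, margin 0.10 and one-sided alpha 2.5% (Protocol 9.5 and Table 22); Control rates of 70, 50, 35 and 25% from Table 22; cited range 35.3 to 60.9% from its footnote. The Co-Ad rate is not given. Write p1 for the Control SCR, d for the Co-Ad deficit, and p2 = p1 − d.

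**Formula** (normal approximation, unpooled variance):

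power = Φ( (0.10 − d) / √[(p1(1−p1) + p2(1−p2)) / 462] − 1.96 )

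**Step 1: reproduce the plan's figures with d = 0.**

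- p1 = 0.50: SE = √(0.50/462) = 0.0329; 0.10/0.0329 = 3.04; Φ(3.04 − 1.96) = Φ(1.08) = 86.0%. Stated: 86.1%.
- p1 = 0.70: SE = √(0.42/462) = 0.0302; Φ(3.317 − 1.96) = 91.3%. Stated: 91.3%.
- p1 = 0.35: SE = √(0.455/462) = 0.0314; Φ(3.187 − 1.96) = 89.0%. Stated: 89.0%.
- p1 = 0.25: SE = √(0.375/462) = 0.0285; Φ(3.510 − 1.96) = 93.9%. Stated: 93.9%.

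Full binomial enumeration of the Miettinen-Nurminen score test, which matches the planned interval, gives 91.3, 86.1, 89.0 and 94.0% in the same order. With d = 0.005 the formula gives 88.2, 82.3, 85.8 and 91.7%, which does not match. The tables therefore assume equal true rates.

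**Step 2: contrast with the titer endpoints.** SD 0.6, so SE = 0.6 × √(2/462) = 0.0395. With the 1.05 ratio: (0.1761 − 0.0212)/0.0395 − 1.96 = 1.96, power 97.5%, as in Table 21. Without it: 0.1761/0.0395 − 1.96 = 2.50, power 99.4%. The titer power does include the interference.

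**Step 3: how fast SCR power falls.** The deficits are illustrative assumptions; the documents give none.

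| Control SCR | d = 0 | d = 0.5 point | d = 1 point | d = 2 points |
|---|---|---|---|---|
| 25% | 93.9 | 91.7 | 88.9 | 81.3 |
| 35.3% | 88.9 | 85.7 | 81.9 | 72.6 |
| 50% | 86.0 | 82.3 | 78.1 | 68.2 |
| 60.9% | 87.6 | 84.0 | 79.9 | 69.9 |
| 70% | 91.3 | 88.2 | 84.4 | 74.8 |

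For example, at 50% with d = 0.01: SE = √((0.2500 + 0.2499)/462) = 0.0329; Φ(0.09/0.0329 − 1.96) = Φ(0.776) = 78.1%. Enumeration of the score test at d = 1 point gives 82.0, 78.3 and 80.4% at Control SCRs of 35.3, 50 and 60.9%.

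**Step 4: how much slack there is.** The deficit at which power reaches 86% is 1.4 points at a Control SCR of 25%, 0.5 at 35%, essentially zero at 50%, 0.2 at 60.9% and 0.8 at 70%. The 86% figure thus tolerates a small deficit away from 50%. It also holds if the Co-Ad SCR is the higher one. At 50% it has no room.

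**Step 5: what depends on the figure.** The planned interval, the 10% criterion and the alpha do not use it. The 514 per group are justified in Protocol 9.5 by the number evaluable for the primary objectives.

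**The case for a change.** The strongest case for a change is consistency. The sponsor chose to allow for interference in one table and not in the next, for HI responses to the same strains. The SCR comparison keeps a formal 10% criterion, and the plan publishes a power for it without saying what that power is conditional on. At a Control SCR of 50%, inside the cited range, any deficit takes power below the stated figure. A short label would cost almost nothing.

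The facts in that case stand: the assumption is unstated, and there is no slack at 50%. The inference is weaker. The 1.05 ratio is applied only to titers, and a titer ratio does not determine a difference in a dichotomised endpoint. Converting one to the other needs a model and an SD of the log10 fold-rise, and the documents give neither. If one assumes a uniform shift on a normal log10 fold-rise with an SD of 0.4 to 0.6, the deficit is about 1.3 to 2.1 points and power about 67 to 79% over the cited range. Those figures rest on choices made outside the documents, and the model ignores both the separate rule for pre-dose titers below 1:10 and the two-fold dilution steps. They show sensitivity, not a contradiction in the plan.

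Nor does the text offer 86% as an unconditional floor. It calls the power nominal and ties it to the plausible rates. A table with one rate per row and a margin is most naturally read as a common rate in both groups, and the arithmetic confirms that reading at once.

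**Conclusion.** No change is needed. Every SCR power in Protocol Table 22 and SAP Table 4 is correct to within about 0.1 point for equal true SCRs, the conventional assumption for such a table. What is missing is a label, and a statistician reading the tables can supply it.

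The sensitivity is real: about 78 to 82% over Control SCRs of 35.3 to 60.9% if the Co-Ad SCR is 1 point lower, and about 68 to 73% if it is 2 points lower, against about 86 to 89% with equality. Both deficits are assumptions made for this check; the calculation otherwise takes 462 per group, a 10-point margin and one-sided 2.5% from the plan. Anyone interpreting a narrow miss on SCR should keep those figures in mind. The comparison is nevertheless secondary and descriptive, and the sample size, alpha, testing sequence and primary power are untouched. Stating the assumption would change no result and no conclusion.

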10. SUPPORTING DOCUMENTATION AND OPERATIONAL CONSIDERATIONS

10.1. Appendix 1: Regulatory, Ethical, and Study Oversight Considerations

10.1.1. Regulatory and ethical considerations

- This study will be conducted in accordance with the protocol and with:
 - Consensus ethical principles derived from international guidelines including the Declaration of Helsinki and Council for International Organizations of Medical Sciences (CIOMS) International Ethical Guidelines.
 - Applicable International Council on Harmonization (ICH) Good Clinical Practice (GCP) Guidelines.
 - Applicable laws and regulations.
- The protocol, protocol amendments, ICF, IB, and other relevant documents (e.g., advertisements) must be submitted to an IEC/IRB by the investigator for review and approval. These documents will be signed and dated by the investigator before the study is initiated.
- Any protocol amendments will require IEC/IRB approval before implementation of changes made to the study design, except for changes necessary to eliminate an immediate hazard to study participants.
- GSK will provide full details of the above procedures to the investigator, either verbally, in writing, or both.
- The investigator will be responsible for the following:

- Providing written summaries of the status of the study to the IEC/IRB annually or more frequently in accordance with the requirements, policies, and procedures established by the IEC/IRB.
- Notifying the IEC/IRB of SAE(s) or other significant safety findings as required by IEC/IRB procedures.
- Providing oversight of the conduct of the study at the site and adherence to requirements of 21 CFR, ICH guidelines, the IEC/IRB, European regulation 536/2014 for clinical studies (if applicable), and all other applicable local regulations.

10.1.2. Financial disclosure

Investigators and sub-investigators will provide the sponsor with sufficient, accurate financial information as requested to allow the sponsor to submit complete and accurate financial certification or disclosure statements to the appropriate regulatory authorities. Investigators are responsible for providing information on financial interests during the study, and for 1 year after completion of the study.

10.1.3. Informed consent process

The investigator or his/her representative must fully explain the nature of the study to the participant and answer all questions regarding the study.

Participants must be informed that their participation is voluntary.

Freely given and written/witnessed informed consent must be obtained from each participant and participant informed assent, as appropriate, prior to participation in the study.

The content of the informed consent form (ICF) must meet the requirements of 21 CFR 50, local regulations, ICH guidelines, Health Insurance Portability and Accountability Act (HIPAA) requirements, where applicable, and the IEC/IRB or study center.

The medical record must include a statement that written, or witnessed informed consent was obtained before the participant was enrolled in the study and the date the consent was obtained. The authorized person obtaining the informed consent must also sign the ICF.

Participants must be re-consented if a new version of the ICF(s) or an ICF addendum is released during their participation in the study.

A copy of the ICF(s) must be provided to the participants.

10.1.4. Data protection

Participants will be assigned a unique identifier by the sponsor. Any participant records or datasets transferred to the sponsor will contain only the identifier. Name and any other information which would identify the participant will not be transferred.

GSK will ensure protection of the personal data of the investigator and site staff which is collected within the framework of and for the purpose of the study, in accordance with the Data Privacy Notice that will be sent to the site staff.

The participants must be informed that:

- His/her personal study-related data will be used by the sponsor in accordance with local data protection law.
- His/her medical records may be examined by Clinical Quality Assurance auditors or other authorized personnel appointed by the sponsor, by appropriate IEC/IRB members, and by inspectors from regulatory authorities.

The participants must be notified about their rights regarding the use of their personal data in accordance with the data privacy section of the ICF.

10.1.5. Committees structure

GSK will obtain favorable opinion/approval to conduct the study from the appropriate regulatory agency, in accordance with applicable regulatory requirements, prior to a site initiating the study in that country. This includes IECs/IRBs for review and approval of the protocol and subsequent amendments, ICF and any other documentation.

Safety oversight will be provided by an SRT composed of GSK RSV OA project team members.

